4.3.5. Safety

All subjects who were administered any test article excluding subjects who drop out prior to administering any test article. At least one observation for safety endpoints should be recorded (e.g. ocular symptom, slit-lamp finding, etc.) or on after treatment start date.

Subjects will be analyzed as per treatment received.

4.4. Handling of Missing Data

For the primary endpoint (visual acuity logMAR score), a sensitivity analysis will be conducted to explore the impact of missing data. This sensitivity analysis rely on an assumption that the missing data are missing at random (MAR) i.e., that the probability that an observation is missing can depend on observed data but is unrelated to the data not observed.

The sensitivity analysis will be based on multiple imputation analysis explained in section 8. Observed missing data are detailed in Appendix 12.2: Missing data pattern.

5. Subject Disposition

A disposition of subjects including the number and percentage of subjects enrolled, subjects adhering to protocol (PP population), subjects treated (safety population), subjects completed, subjects discontinued from the study and subjects enrolled but not dispensed will be summarized by the 2 treatment groups. In addition subjects enrolled but not randomized will be also included (where relevant).

Subjects will be allocated to one of the three mutually exclusive groups:

- Completed: Subjects are considered to have completed the study if (1) they are eligible, (2) not discontinued, (3) they have completed all visits including the final visit (Visit 2).
- Discontinued: Subjects are considered to have discontinued from the study if (1) test article administered and (2) discontinued because of one of the following reasons:
 - Adverse Event;
 - Unsatisfactory Visual Response due to test article;
 - Unsatisfactory Lens Fitting due to test article;
 - Lens Discomfort;
 - Lens Handling Difficulties;
 - Withdrew Consent during study;
 - Lost to Follow Up;
 - Subject no longer meets Eligibility Criteria;
 - Subject Withdrawn by PI due to non-compliance to protocol;

- Test Article No Longer Available;
 - Other.
- Enrolled but Not Dispensed: Subjects are considered Enrolled but Not Dispensed if they provide informed consent but (1) failed to satisfy the eligibility criteria (inclusion/exclusion criteria) or (2) were randomized but test article was not administered for any reason.

Total Enrolled = Completed + Discontinued + Enrolled Not Dispensed.

The reasons for study discontinuation and study withdrawal will also be summarized.

All percentages will be based on the number of total enrolled subjects.

5.1. Protocol Deviations

Any protocol deviation that could impact the primary endpoints will result in the subject being excluded from the Per-Protocol analysis population. No analysis on protocol deviations will be performed. Protocol deviations that lead to exclusion from PP population will be listed.

6. Demographics and Baseline Characteristics

The demographic characteristics and the baseline characteristics will be summarized for All Enrolled subjects and for PP analysis set.

Individual subject listings will be provided for all the enrolled subjects to support the summary tables.

6.1. Demographics

Demographic characteristics will be collected at Visit 1 and will be summarized by treatment arm. These are: Age, gender, race and ethnicity.

Age at informed consent will be used only to check the inclusion criteria no.3, i.e. subject must be between 18 and 39 (inclusive) years.

In the demographic characteristics summary, age will be derived as integer part of (first study visit date – date of birth + 1) / 365.25.

6.2. Baseline Disease Characteristics

The following baseline clinical characteristics will be summarized at subject level by treatment arm:

- CLUE™ Baseline Handling Questionnaire;

- Entrance distance Snellen Visual Acuity with their habitual contact lens correction in place.

6.3. Medical History

Past and concomitant medical history will be summarized by treatment separately, but they will be listed together.

6.4. Other Background Information

Habitual Contact Lens Information will be collected at Visit 1 and will be summarized by treatment.

The following Habitual Contact Lens Information will be reported at eye level:

- Lens type
- Sphere
- Monovision Distance Lens (yes/no/not-applicable)

While the remaining information will be reported at subject level:

- Lens Care Regimen
- Modality
- Cleaning
- Duration of the prescription (days) = Visit 1 Date - Approximate Prescription Date + 1.

In case of partial prescription date (where UK and UKN indicate unknown or missing day and month respectively):

- UK-MMM-YYYY: Assume 01-MMM-YYYY;
- UK-UKN-YYYY: Assume 01-JAN-YYYY.

7. Treatments and Medications

7.1. Prior and Concomitant Medications

Concomitant medications will be documented during screening and updated during the study.

Disallowed medications or any concomitant therapies that are disallowed for this study include: Any ocular medications or any systemic medications that (e.g., chronic steroid use) that are known to interfere with contact lens wear.

Prior and concomitant medications, will be coded using the WHO Drug Dictionary Enhanced Version WHODDRUG SEP 2017.

A prior medication is defined as a medication where both the start and end dates are before the date of first test lens insertion following randomization.

A concomitant medication is defined as one where the end date is either on or after the date of first test lens insertion following randomization or is missing. The start date of a concomitant medication can be before or after the date of the first test lens insertion following randomization. For a medication with partial or completely missing onset date, unless it can be determined to be “prior to the first test lens insertion following randomization” from the incomplete start date or end date (e.g., month, year is before the first test lens insertion date, or end date is before the first test lens insertion date), the medication will always be assumed to be concomitant. Medications initiated prior to the start of study treatment and continued after the start of study treatment will be counted as both prior and concomitant medications.

For the purpose of inclusion in prior and/or concomitant medication tables, incomplete medication start and stop dates will be imputed as follows:

Missing start dates (where UK, UKN and UNKN indicate unknown or missing day, month and year respectively):

- UK-MMM-YYYY: Assume 01-MMM-YYYY. If the month and year are the same as the first dose of study drug month and year, then assume the date of first dose of study drug;
- UK-UKN-YYYY: If the year is prior to the year of first dose of study drug, assume 01-JAN-YYYY of the collected year. If the year is the same as the first dose of study drug year, then assume the date of first dose of study drug;
- UK-UKN- UNKN: Assume date of first dose of study drug.

Missing stop dates for concomitant medications data will be handled as follows (where UK, UKN and UNKN indicate unknown or missing day, month and year respectively):

- UK-MMM-YYYY: Assume the last day of the month;
- UK-UKN-YYYY: Assume 31-DEC-YYYY;
- UK-UKN- UNKN: Assume ongoing and leave it missing.

The total number of concomitant medications and the number and percentages of subjects with at least one concomitant medication will be summarized for both Randomized and PP analysis sets including also the number and percentages of subjects by preferred name, in descending order of frequency in the total column.

A listing for both prior and concomitant medications will be created for all the enrolled subjects.

7.2. Study Treatments

Study treatment will be dispensed to subjects meeting all eligibility requirements, including any dispensing requirements set forth in this clinical protocol. Subjects will be dispensed an adequate supply of test articles to complete the study.

The treatment (K-Lens or Placebo) will be daily self-administered by subjects for the whole duration of the study (6-9 days). Subjects must wear the lenses for at least 8 hours per day.

7.2.1. Treatment Compliance and Extent of Exposure

The treatment compliance will be assessed at follow-up visit (Visit 2) at eye level. The following information will be summarized by treatment at subject level for both subjects in PP and safety population:

- Number of days wearing the lens
- Wearing time on Visit 2 (hours)

The number of subjects not wearing the lens at Visit 2 will be tabulated at subject level by treatment for subjects in safety population.

No modification to the daily treatment regimen is planned.

8. Efficacy Analysis

All the efficacy analyses will be conducted on PP population comparing K-Lens against Placebo.

As supportive analysis, the efficacy analysis will be repeated on the mITT population regardless of missing data.

In addition, a sensitivity analysis will be conducted on the primary endpoint using the mITT population to assess the impact of missing data using a multiple imputation (MI) process. Missing values for visual acuity logMAR score will be imputed from a regression model with treatment group, analysis site and logMAR score at Visit 1 and Visit 2 as covariates. Twenty imputations²⁸ will be performed using SAS PROC MI with the Fully Conditional Specification (FCS) option to take into account non-monotone missing data pattern (see Appendix 12.2: Missing data pattern). In case the pattern of missing data will be monotone, the procedure will use an imputation method for data sets with monotone missingness. The adjusted means difference between treatments and its standard error will be displayed with corresponding two-sided 95% CI and non-inferiority flag calculated using the SAS MIANALYZE procedure to combine the results of the analyses performed by imputation. See Appendix 12.3 for the SAS PROC MI, PROC MIXED and PROC MIANALYZE specifications.

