1.16	Lens Power Modification (if applicable)	
Adjust the lens power if the subject's best sphere over-refraction is not plano.
 
One power modification is allowed. If the subject's best sphere over-refraction is not plano, the subject will have to return no sooner than the following day, since subjects are not allowed to wear more than one lens per eye per day. When a subject returns for another lens, new baseline information must be recorded (starting with step 1.7), and then proceed per protocol through the remaining Visit 1 steps.
	
1.17	Subject Reported Ocular Symptoms	Subjects will respond to a verbal open-ended symptoms questionnaire.	
1.18	Subjective Lens Fit Assessment	
Evaluate overall lens fit acceptance (acceptable or unacceptable) based on centration, movement and other fitting characteristics.
 
An unacceptable fit is deemed by one of the following criteria:
 
 • limbal exposure at primary gaze or with extreme eye movement; • edge lift; • excessive movement in primary and up gaze; or • insufficient movement in all three of the following conditions: primary gaze, up gaze, and push up test. 
Note: if lens fit is unacceptable subject will be discontinued from the study.
	
1.19	Distance ETDRS LogMAR Visual Acuity	
Perform monocular distance ETDRS LogMAR visual acuity test at a 4-meter distance over the test eye only under the following condition:
 
 • bright illumination (e.g., >400 lux), high luminance, with high contrast charts (HLHC); 
The Precision Vision 4-meter high contrast ETDRS charts (Chart 1 and Chart 2) will be used.
 
One measurement will be recorded per eye.
	

1.20	Exit Snellen VA	Record subjects' distance visual acuity, OD, OS and OU to the nearest letter. [REDACTED]	
1.21	Continuance	For the subject to continue in the study, they must meet all three of the following criteria: 
 • Visual acuity is 20/30 or better OD and OS • The lens fit is acceptable OD and OS • Investigator approval. If the Investigator does not approve the dispensing of the first study lens, then the study is terminated for that subject. 	

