3.2.2. Secondary Endpoints

FDA Biomicroscopy Scale

This secondary endpoint is a binary response measured at eye level over the post-fit period including unscheduled visits between Visit 1 and Visit 2:

- Yes = eye has at least one clinically significant (Grade 3 or Grade 4) slit lamp finding;
- No = otherwise.

An eye with multiple clinically significant slit lamp finding events will be counted only once.

The FDA Biomicroscopy Scale measures the severity of the ocular clinical findings and goes from Grade 0 (none) to Grade 4 (severe). The procedure is explained in the [REDACTED] in Appendix D of the study protocol. The individual ocular finding results are considered as other endpoints, these are described in section 3.2.3 Slit-lamp findings.

Unacceptable Lens Fitting

This secondary endpoint is a binary response (yes/no) measured at eye level at fitting and post-fitting evaluations including unscheduled visits:

- Unacceptable = unacceptable fit due to meeting one of the following criteria:
 - limbal exposure at primary gaze or with extreme eye movement;
 - edge lift;
 - excessive movement in primary up gaze;

- insufficient movement in all three of the following conditions: primary gaze, up gaze, and push up test.
- Acceptable = otherwise.

This will be recorded on the eCRF as whether the fit is unacceptable or not.

Subjects discontinued because of unacceptable fitting will also be counted as having an Unacceptable response. An eye with multiple unacceptable fitting events will be counted only once.

The procedure is explained in the [REDACTED] in Appendix D of the study protocol. The individual lens fitting characteristics are considered as other endpoints, these are described in section 3.2.3 Lens Fitting Characteristics.

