4.3.4. Per Protocol (PP)

Per Protocol Analysis set will be the primary analysis population. It will include all subjects who have successfully completed all visits and did not substantially deviate from the protocol as determined by the trial cohort review committee prior to database hard lock. Justification of excluding subjects with protocol deviations in the per-protocol population set will be documented in a memo to file.

Subject will be analyzed as per randomized treatment.

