8.2.4. Unacceptable Lens Fitting

Proportion of eyes with unacceptable fitting recorded at any evaluation performed on or after the first fitting is a secondary endpoint and will be summarized by treatment arm.

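### SAP Section 8 makes per-protocol the main set for unacceptable lens fit (8.2.4), so the main summary omits every fit failure found at Visit 1

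*SAP*

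**What the plan says.** **Analysis set.** SAP Section 8: "All the efficacy analyses will be conducted on PP population comparing K-Lens against Placebo". The same section repeats the efficacy analyses on mITT as supportive. Section 8.2.4 sits under Other Efficacy Endpoints and names no set of its own. PP (SAP 4.3.4) is defined thus: "It will include all subjects who have successfully completed all visits and did not substantially deviate from the protocol".

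**Endpoint.** SAP 8.2.4: "Proportion of eyes with unacceptable fitting recorded at any evaluation performed on or after the first fitting is a secondary endpoint". SAP 3.2.2 adds two counting rules: "Subjects discontinued because of unacceptable fitting will also be counted as having an Unacceptable response" and "An eye with multiple unacceptable fitting events will be counted only once".

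**Conduct.** In Protocol 7.2, the lens is assigned at step 1.12, inserted at 1.13 and graded for fit at 1.18. Step 1.18 carries the instruction "Note: if lens fit is unacceptable subject will be discontinued from the study", and step 2.8 repeats it at Visit 2. Continuance at step 1.21 also requires: "The lens fit is acceptable OD and OS".

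**Protocol rule.** Protocol 14.6 would summarise secondary endpoints on whatever data are available, unscheduled visits included. SAP Section 1 says the SAP overrides protocol Section 14 where they differ.

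**The concern.** For a fit failure at Visit 1, exclusion from PP follows from the outcome itself. The subject is removed from both numerator and denominator of the main summary, and the rule in 3.2.2 that counts fit discontinuations as Unacceptable cannot operate for that subject. The SAP thus defines the endpoint to include these events and then makes a set that cannot contain them the main one. In doing so it displaces the protocol's broader rule for secondary endpoints.

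What is at stake is the reported fit-failure rate of lenses from the new manufacturing line. Fit is one of only two secondary endpoints in Protocol 2.2. The summary that follows the SAP's own counting rule is the one labelled supportive.

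**Working it through.** The plan gives no fit-failure rate and no figure for this endpoint, so there is nothing to reproduce. The rates below are assumptions, set against the planned 88 K-Lens and 44 Placebo subjects randomised (Protocol 4.3).

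**1. Set membership**

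- *Failure at Visit 1.* Randomised, lens inserted, discontinued at 1.18, fails 1.21, no Visit 2. Outside PP with certainty. Inside mITT if insertion counts as administration.
- *Failure at Visit 2.* Discontinued by step 2.8, but PP membership is unclear. For exclusion: the word successfully in the PP definition, Protocol 8.1, and SAP Section 5 ("Subjects are considered to have completed the study if (1) they are eligible, (2) not discontinued, (3) they have completed all visits"). For inclusion: the PP definition does not refer to Completed status, Protocol 8.2 has the investigator finish the current visit, and the only fit item among the Protocol 8.2 reasons concerns subjects not successfully dispensed.

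**2. Rates with no other attrition**

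Let N be randomised subjects with a lens inserted, F all fit failures and v those at Visit 1.

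- mITT = F/N
- PP, Visit 2 failures kept = (F − v)/(N − v)
- PP, Visit 2 failures excluded = 0/(N − F), counting scheduled visits only

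Subject-level results for K-Lens, N = 88:

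| F | v | mITT | PP, Visit 2 failures kept | PP, Visit 2 failures excluded |
|---|---|---|---|---|
| 2 | 2 | 2/88 = 2.3% | 0/86 = 0% | 0/86 |
| 2 | 1 | 2/88 = 2.3% | 1/87 = 1.1% | 0/86 |
| 2 | 0 | 2/88 = 2.3% | 2/88 = 2.3% | 0/86 |
| 8 | 8 | 8/88 = 9.1% | 0/80 = 0% | 0/80 |
| 8 | 4 | 8/88 = 9.1% | 4/84 = 4.8% | 0/80 |
| 8 | 0 | 8/88 = 9.1% | 8/88 = 9.1% | 0/80 |

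The F = 8 rows are a deliberately high case, since 8 is the whole planned K-Lens loss (88 − 80).

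The endpoint is counted by eye. For F = 2, v = 1 with Visit 2 failures kept, both eyes failing gives mITT 4/176 = 2.3% against PP 2/174 = 1.1%. One eye failing gives 2/176 = 1.1% against 1/174 = 0.6%.

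**3. Rates with other attrition**

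Let d further subjects be outside PP, none with a fit failure, and keep Visit 2 failures in PP. Then PP = (F − v)/(N − v − d). Rearranging, PP is below mITT exactly when F/N < v/(v + d).

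With v = 1 and d = 7, the threshold is 1/8 = 12.5%. Writing w for Visit 2 failures, PP = w/80 and mITT = (w + 1)/88.

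- w = 2: PP 2/80 = 2.5%, mITT 3/88 = 3.4%
- w = 10: PP 10/80 = 12.5%, mITT 11/88 = 12.5%
- Above w = 10, PP is the higher of the two.

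With d = 0 the condition is F/N < 1, so PP is too low whenever v > 0, short of every subject failing.

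**The case against.** The strongest reply is that nothing is hidden. The mITT repeat is planned. SAP 9.6 tabulates fit acceptability at fitting and at one week in the safety population, and the disposition table lists unsatisfactory fitting as a reason. If fit is graded only at steps 1.18 and 2.8, no eye can fail twice, so the two visits in 9.6 add up to the 3.2.2 numerator. The endpoint has no test or decision rule. All of this stands, and it is why the point is minor. It does not make the summary labelled main agree with the endpoint's own definition.

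mITT is not a perfect benchmark either. Because 3.2.2 treats everything not unacceptable as acceptable, a subject who drops out for another reason before Visit 2 can count as acceptable.

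A reader might infer three stronger claims that the documents do not support:

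- *That PP must read 0% at any true rate.* This needs Visit 2 failures to be excluded, which is unsettled, and no fit grading at unscheduled visits. Steps U.1 to U.7 list none, but Protocol 7.3 describes a minimum data set and SAP 3.2.2 includes unscheduled visits in the endpoint. A failure found there carries no stated discontinuation rule, so that subject could still reach Visit 2 and PP.
- *That PP is biased low in every case.* Step 3 of the working shows that it is not once other dropouts are allowed.
- *That the slit-lamp endpoint (8.2.3) should move too.* Scheduled grading at Visit 1 is step 1.10, before insertion, and neither the rest of Visit 1 nor the final evaluation lists another. Since SAP 9.3 reads no noted finding as Grade 0, adding Visit 1 fit failures could dilute that rate.

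**Conclusion.** The concern holds in limited form. It is certain from the text that the main summary for 8.2.4 omits every Visit 1 fit failure. With no other attrition, the PP rate is too low whenever such a failure occurs. With other dropouts it is too low at low failure rates, which are the plausible ones in habitual wearers (an assumption), but not always. If Visit 2 failures are also excluded, PP shows none of the failures found at scheduled visits. If no failure occurs at Visit 1, Visit 2 failures stay in PP and there is no other attrition, PP and mITT agree.

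The size cannot be fixed from the documents. At 2 failures in 88, the gap is between 0 and 2.3 percentage points. The direction of any error in the difference between arms cannot be stated in advance. Severity is minor, and the primary non-inferiority analysis is unaffected.

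**What to change.** In SAP Section 8, state that for 8.2.4:

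- the main summary is on mITT by randomised arm;
- it uses all evaluations from first fitting onward, unscheduled visits included, with the 3.2.2 counting rules;
- insertion of a study lens at Visit 1 counts as administration;
- the PP summary is supportive.

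The administration clause is needed because the term is undefined. Protocol 6.3 uses it for dispensing. SAP Section 5, however, lists unsatisfactory fitting among reasons that presuppose administration, and SAP 7.1 and 9.1 count from lens insertion. Insertion is therefore the natural reading. A further sentence in SAP 4.3.4 saying whether a Visit 2 fit failure belongs to PP would make the supportive summary interpretable.

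Leave 8.2.3 and all other endpoints as they are. The cost is one or two sentences and no new tables or data. The reported fit-failure rate may look slightly less favourable.

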8.1. Primary Efficacy Endpoint

Primary analysis will be run on monocular contact lens-corrected distance visual acuity using a logMAR visual acuity scale measured at follow-up visit (Visit 2) for each eye.

This will be analyzed using a linear mixed effects model to test for non-inferiority of K-Lens relative to Placebo. LogMar score is assumed to be normally distributed and this will be verified visually with a QQ-plot of residuals, using the stored SAS output obtained from fitting the linear mixed model, and tested with a normality test. Lens group will be included as fixed effects in the model and investigator site as random effect.

Let y_{ijkl} be the visual acuity measured on the i th eye, $i = [\text{Left, Right}]$, of the j th subject, $j = 1, 2, \dots, n_l$, assigned to the k th treatment, $k = 1, 2$, in the l th investigational site, $l = 1, 2, \dots, 5$. The proposed statistical model for the primary analysis is

$$y_{ijkl} = \mu + Treatment_k + Site_l + \varepsilon_{i(jkl)}, \text{ where}$$

- μ : overall mean;
- $Treatment_k$: effect of the k^{th} treatment, a fixed effect;
- $Site_l$: effect of the l^{th} investigational site, a random effect;
- $\varepsilon_{i(jkl)}$: random error associated with the i^{th} eye of the j^{th} subject assigned to the k^{th} treatment in the l^{th} investigational site.

Here we assume $site_l$ and $\varepsilon_{ij(kl)}$ are independent and

- $site_l \sim N(0, \sigma_{site}^2)$;
- $\begin{bmatrix} \varepsilon_{Left(jkl)} \\ \varepsilon_{Right(jkl)} \end{bmatrix} \sim N \left(\begin{bmatrix} 0 \\ 0 \end{bmatrix}, \begin{bmatrix} \sigma_{11}^2 & \sigma_{12} \\ \sigma_{21} & \sigma_{22}^2 \end{bmatrix} \right)$.

While the site effect and the error term will have a diagonal covariance matrix, there will be a correlation between the visual acuity of eyes belonging to the same subject. The model will take this into account using an unstructured covariance matrix (UN) between left and right eye. Should the estimation algorithm not converge, then a Compound Symmetry matrix (CS) will be used. In this case, the assumption is that observations coming from different eyes will have the same variance.

$$\begin{bmatrix} \varepsilon_{Left(jkl)} \\ \varepsilon_{Right(jkl)} \end{bmatrix} \sim N \left(\begin{bmatrix} 0 \\ 0 \end{bmatrix}, \begin{bmatrix} \sigma^2 & \sigma_{12} \\ \sigma_{21} & \sigma^2 \end{bmatrix} \right)$$

The log-likelihood ratio test will be used to test for the homogeneity between the residual covariance structures across treatment groups. The Kenward and Roger method will be used to calculate the denominator degree of freedom.²⁵

The null and alternative hypotheses for non-inferiority of K-Lens relative to Placebo are as follows:

$$H_0: \Delta \geq 0.1$$
$$H_A: \Delta < 0.1$$

where Δ is the mean difference in visual acuity between K-Lens and Placebo (K-Lens minus Placebo). The non-inferiority test will be based on the least-square mean difference (K-Lens minus Placebo) and corresponding 95% confidence interval calculated using the final selected model. The upper bound of the 95% confidence interval will be compared to the non-inferiority margin of 0.1 LogMAR. If the upper bound is less than 0.1, K-Lens will be considered non-inferior to Placebo with respect to visual acuity.

The following code will be used to run the mixed model.

```
proc glimmix data = dataset plots=ResidualPanel;
class treatment siteid subjid eye;
model logmar = treatment/ DDFM=KenwardRoger S;
random intercept /subject = siteid;
random eye / type=matrix_cov subject=subjid(siteid) group = treatment
residual;
lsmeans treatment / diff=control('Placebo') cl;
covtest 'Common Variance' Homogeneity;
ods output ParameterEstimates=parms Covtests=mixcovtest
CovParms=mixcovp diffss=diffs lsmeans=lsmeans;run;
```

Where:

- “Treatment” is the treatment group variable (K-Lens/Placebo);
- “Siteid” is the investigator site identifier;
- “Eye” is the variable to identify which eye the observation belongs to (left/right);
- “Subjid” is the subject identifier;
- “Matrix_cov” is the covariance structure (UN/CS) between the left eye visual acuity and right eye visual acuity.

If the hypothesis of homogeneity is accepted (chi-square test p-value > 0.05) the syntax “group = treatment” and the ‘covtest’ statement will be omitted from the final model.

